8.2 Exclusion Criteria

Individuals meeting any of the following criteria at the Screening Visit are ineligible to participate in this study:

- 1. Have participated in any clinical trial with an investigational drug/device within 2 months before the Screening Visit and throughout the study duration.
- 2. Have a known hypersensitivity to one of the components of the study drug or procedural medications (eg, fluorescein), including to a compound chemically related to MT8.
- 3. Have a presence or history of any ocular or systemic disorder or condition that might hinder the efficacy of the study treatment or its evaluation, could possibly interfere with the interpretation of study results, or could be judged by the investigator to be incompatible with the study visit schedule or conduct (eg, progressive or degenerative corneal or retinal conditions, lagophthalmos, uveitis, optic neuritis, poorly controlled diabetes, autoimmune disease, systemic infection, neoplastic diseases), or that may compromise the safety of the patient.
- 4. Have a significant history of alcohol abuse or drug/solvent abuse (within the last 2 years).
- 5. Be unwilling to comply with any study assessments or procedures.
- 6. Be a woman who is pregnant, nursing or planning a pregnancy.
- 7. Be a woman of childbearing potential who is not using a highly effective method of birth control. For non-sexually active females, true abstinence (when in line with the preferred and usual lifestyle of the subject) may be accepted as an adequate method of birth control; however, if the patient plans to become sexually active during the study, she must agree to use adequate birth control as defined above for the remainder of the study and for 4 weeks after the end of study treatment. ¹⁹ For the definition of childbearing potential and list of highly effective methods of contraception, see APPENDIX 1.
- 8. Be a male patient who is not permanently sterile and who is not willing to use condoms during the study and for 4 weeks after the end of study treatment. Male patients whose partners are not of childbearing potential are not required to use condoms.

For the study eye:

- 9. Have any active ocular infection (bacterial, viral, fungal or protozoal) or active inflammation not related to NK in the study eye.
- 10. Have any other ocular disease requiring topical ocular treatment in the study eye during the course of the study treatment period, except for glaucoma if treated by preservative-free eye drop (single-agent treatment, once daily, stable regimen 4 weeks before screening and during the study).
- 11. Receive topical ophthalmological treatments other than the study drug provided by the study Sponsor and the treatments allowed by the study protocol (eg, preservative-free artificial tears; preservative-free eye drop (single-agent treatment, once daily, stable regimen 4,weeks before screening and during the study) for glaucoma; topical antibiotics; other than tetracycline; see Section 9.6.1).
- 12. Have severe blepharitis and/or severe meibomian gland disease in the study eye.

- 13. Have severe vision loss in the study eye with no potential for visual improvement in the opinion of the investigator as a result of the study treatment.
- 14. Have evidence of corneal ulceration/melting involving the posterior third of the corneal stroma, or perforation in the study eye.
- 15. Have a history of any ocular surgery (including laser or refractive surgical procedures) within 3 months before the Screening Visit in the study eye. An exception to the preceding statement will be allowed if the ocular surgery is considered to be the cause of the Stage 2 or 3 NK. Ocular surgery will not be allowed during the study treatment period and elective ocular surgery procedures in the study eye should not be planned during the duration of the study.
- 16. Have a history of corneal transplantation in the study eye performed less than 12 months prior screening.
- 17. Have had prior surgical procedures for the treatment of NK (eg, complete tarsorrhaphy, conjunctival flap, etc.) except partial tarsorrhaphy if done more than 6 months prior to screening visit (with investigators assessment documenting that the eye lids are functioning sufficiently to ensure adequate protection of the eye) and amniotic membrane transplantation, if at least 2 weeks after the membrane has disappeared within the area of the PED or corneal ulcer (and at least 6 weeks after the procedure) in the study eye.
 - Patients previously treated with Botox® (Botulinum toxin) injections used to induce pharmacologic blepharoptosis are eligible for enrolment only if the last injection was given at least 3 months before the Screening Visit.
- 18. Use therapeutic contact lenses or wear contact lenses for refractive correction during the study treatment periods in the eye(s) with NK.
- 19. Have an anticipated need for punctal occlusion during the study treatment period. Patients with punctal occlusion or punctal plugs inserted before the study are eligible for enrolment provided that the punctal occlusion is maintained during the study.
- 20. Have an uncontrolled glaucoma at the Screening Visit. Patients suffering from glaucoma requiring ophthalmic drops for topical treatment at the Screening Visit or during the study are not eligible, except if the ophthalmic drops is a preservative-free treatment administered maximum once daily as a single-agent treatment and at a stable regimen 4 weeks before screening and at the same dose during the study. Patients treated with oral intraocular pressure-lowering drugs at the Screening Visit and during the study may be enrolled if their glaucoma status is assessed as stable and controlled.

For the fellow eye:

21. Have Stage 2 or 3 NK or perforation.

For any eye:

- 22. Have a history of ocular cancer.
- 23. Have had prior treatment with Oxervate (cenegermin eye drops).

8.3 Rescreening

Individuals who sign the ICF to participate in the study but who do not subsequently meet all the requirements as outlined in the inclusion and exclusion criteria (screen failures) may be rescreened once, provided the investigator assesses and documents that the patient's condition(s) may evolve in order to allow enrolment.

8.4 Study Withdrawal, Removal, and Replacement of Patients

Withdrawals will not be replaced (neither withdrawals from study drug, nor withdrawals from the study).

8.4.1 Withdrawal from Study Drug

Patients permanently withdrawn from study drug should not be withdrawn from the study and, apart from study drug administration, should continue all scheduled study visits and procedures until the end of the scheduled treatment period at Day 56/Visit 8 (±3 days) to ensure complete follow-up (except in cases where the patient has withdrawn consent for study participation). The Follow-up Visit should take place 4 weeks after Day 56/Visit 8 (±3 days) regardless the date of definitive study drug discontinuation. If this is not possible, patients will be at least asked to return to the study site as soon as possible to complete the Early Termination and Follow-up Visit assessments as indicated in the Schedule of Assessments (Table 2).

If a patient discontinues study drug for any reason, the study site must immediately notify the medical monitor. The date and the reason for discontinuation must be recorded on the electronic case report form (eCRF).

In the event that a patient discontinues study drug prematurely because of a treatment-emergent adverse event (TEAE) or serious TEAE, the TEAE or serious TEAE will be followed up until it resolves (returns to normal or baseline values) or stabilises, or until it is judged by the investigator to no longer be clinically significant.

A patient may be withdrawn from the study drug at any time for reasons including, but not limited to, the following:

- Progressive disease: A rescue treatment may be initiated by the investigator according to clinical judgment as described in Section 9.6.2.
- Unacceptable toxicity or AE
- General or specific changes in the patient's condition that renders him/her ineligible for further treatment according to the inclusion/exclusion criteria (eg, suspected hypersensitivity to the study drug, pregnancy, etc)

Corneal healing is not a reason that study drug should be withdrawn before the end of the 8-week treatment period.

8.4.2 Withdrawal from the Study

Patients may withdraw from the study at any time for any reason without jeopardy or prejudice or compromising their clinical care. However, every effort should be made to adhere to as many study assessments as possible. If a patient indicates that he/she wishes to withdraw from the study, whenever possible, the patient should be seen by the investigator and the procedures for the Early Termination Visit should be performed (refer to Table 2).

A patient may be withdrawn from the study at any time for reasons including, but not limited to, the following:

- Patient withdrawal of consent: At any time, a patient's participation in the study may be terminated at his/her request or on the basis of the investigator's clinical judgment. The reason for patient withdrawal will be noted on the eCRF.
- Patient fails to adhere to the protocol requirements (eg, drug noncompliance, failure to return for study visits).
- Lost to follow-up: The patient did not come for 3 visits, and study personnel were unable to contact the patient for at least 8 weeks.
- Pregnancy, as indicated in Section 12.8
- The investigator also has the right to withdraw patients from the study in the event of intercurrent illness, (S)AEs, and administrative or other reasons. Data for all visits to the point of withdrawal must be recorded in the patient's medical record and in the eCRF.

The data to be collected for patients who withdraw from the study should include:

- Date of withdrawal from the study
- Reason for withdrawal from the study
- Data on assessments conducted (if possible) as part of the Early Termination Visit as described in Table 2
- Data on any (S)AEs present at the time of withdrawal from the study

The investigator will follow patients who are withdrawn from the study as a result of an (S)AE until the event has resolved, subsided, stabilised or until the event is otherwise explained or the patient is lost to follow-up (refer to Section 12.7.4). If withdrawal from the study is a result of a SAE or pregnancy, the SAE/pregnancy will need to be reported and followed up as described in Section 12.7.4 and Section 12.8 respectively.

After study withdrawal, treatment will be decided by the investigator according to clinical judgment and may consist of topical, oral or surgical treatment.

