drop QID) or vehicle, unless the DMC issues a specific recommendation for study conduct related to the safety information on an ongoing basis.

The DMC will confirm in writing that the enrolment and dose escalation to a next dose level can continue based on the safety data received, if any (AESI, SAE, PK).

The DMC can recommend discontinuing the treatment at any time before the formal review of the data from the first 24 patients.

Once the 24th patient has been enrolled, enrolment of new patients will be put on hold and the DMC will perform a formal review of all the safety and PK data available before enrolment of new patients is resumed. The treatment of the first 24 patients will continue as planned. The DMC may also recommend discontinuing the 12-lead ECG assessment in the remaining patients (if no significant systemic exposure to the study drug is observed).

If no study discontinuation or change in the protocol design is recommended after the formal DMC review of all safety data for the first 24 patients, enrolment will resume and patients will be randomised to all 4 treatment arms in a 1:1:1:1 ratio until approximately 27 patients are enrolled in each arm (approximately 108 patients total). Another formal review of the data by the DMC will be conducted 8 weeks after approximately 50% of patients (54 patients) have been enrolled.

During the double-masked treatment period, all patients will administer 1 drop (approximately 25 μ L) REC 0/0559 or vehicle in the study eye QID at 4 hour intervals \pm 30 minutes (starting in the morning) for 8 weeks.

Patients will be followed up for 4 weeks after the end of treatment.

Details related to the DMC are in Section 15.8.

At any time during the study, the investigator can discontinue the study drug and initiate a rescue treatment if clinically required (eg, in the case of worsening of disease).

[figure not shown]
In case of study drug discontinuation for any reason, including when a rescue therapy is started, the patient will be asked to stay in the study and perform all the visits and assessments as planned (except in cases where the patient has withdrawn consent for study participation). Patients who discontinue study drug should at least complete the Early Termination and Follow-up Visits if possible.

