9.5 Treatment Accountability and Compliance

The investigator will be responsible at the site level for maintenance of records of study drug delivered to the study site, the inventory at the study site, the distribution to and use by each patient, and the return of materials to the Sponsor for storage or disposal. These records should include dates, quantities, batch numbers, expiration dates, in-clinic temperature log, and study drug kit numbers assigned.

At each visit after initiation of treatment, study site personnel will record compliance of the patient with the patient's assigned regimen. Patients will be instructed to bring their unused/partially used/empty containers back for inspection at each study visit and the number of opened BFS containers will be recorded. Patients will also be instructed to fill out a paper diary recording the date and time of study drug administration, which should be brought to the site at each study visit and reviewed with the patient. Patients are to be reminded of the importance of compliance with their assigned regimen, with an emphasis on taking their study drug on schedule and maintaining the prescribed interval between doses.

At each study visit during the treatment period, the patient will have to bring back used and unused BFS as well the diary. At Day 3 (± 1 day) Visit, the investigator should review the patient's diary in order to discuss with the patient any issue in compliance so that this is corrected by the Day 7 (± 1 day) Visit.

Patient compliance with the treatment will be assessed at each study visit during the treatment period.

Investigators will maintain records that adequately document that the patients were provided with the correct study drug kits and reconcile the products received from the drug dispensing centre. Study drug will not be returned to the Sponsor until accountability has been fully monitored.

Study drug kits must be returned at each visit, as compliance will be assessed by number of opened BFS containers. Noncompliance is defined as taking less than < 80% or more than 120% of study drug during any outpatient evaluation period (visit to visit). Discontinuation of treatment for noncompliance is at the investigator's discretion and is to be noted on the eCRF.

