7.1. Estimands for the Primary Efficacy Endpoint

The primary efficacy endpoint is the evaluation of the percentage of patients achieving complete corneal healing of PED or corneal ulcer at Week 8, defined as no corneal fluorescein staining in the area of the PED or corneal ulcer as assessed by an independent central reading centre, and the population level summary will be the difference in treatment proportions (common risk difference) at Week 8. The primary estimand for the primary efficacy endpoint will be evaluated in the mITT population, which is patients with stage 2 or stage 3 NK as defined by the inclusion/exclusion criteria who received at least one dose of study drug.

Intercurrent events are events occuring after treatment initiation that affect the interpretation of or the existence of the measurements associated with the clinical question of interest. As more than one intercurrent event is possible, Table 3 lists all potential intercurrent events and the strategy to deal with them.

Table 3: Potential intercurrent events for the primary estimand

Intercurrent Event	Primary estimand: Strategy to Deal With Intercurrent Event Within Analysis	Primary estimand: Assessment of Patient
ICE1: Treatment discontinuation due to treatment-related AE	Composite	Available data observed on or after the occurrence of the ICE will be set to missing and imputed as failure.
ICE2: Treatment discontinuation due to any other reason than treatment-related AE or death	Treatment policy strategy	Available data occurring on or after the ICE will be used for the analysis as observed. Monotone missing data will be imputed using LOCF
ICE3: Prohibited rescue treatments or rescue procedures initiation during the 8 week study treatment administration period	Composite	Available data observed on or after the occurrence of the ICE will be set to missing and imputed as failure.
ICE4: Death	Composite	All monotone missing data will be imputed as failure.

For patients who discontinue treatment due to a treatment-related AE (ICE1), due to strat of prohibited rescue treatments or rescue procedures during the 8 week study treatment administration period or due to death (ICE4) a composite strategy will be applied. All observed data occurring on or after ICE1 and ICE3 will be set to missing and imputed as failure. Prohibited rescue treatment or rescue procedures starting at

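### Protocol 8.4.2 permits withdrawal from the study for drug noncompliance, in conflict with 7.1, 8.4.1 and 9.5, so an obtainable Week 8 reading can be lost

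*Protocol*

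**What the plan says.** Four places in the protocol bear on a patient who does not take the drug as directed.

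- Section 8.4.2 concerns leaving the study altogether. Its list is introduced by "A patient may be withdrawn from the study at any time for reasons including, but not limited to, the following", and one item reads "Patient fails to adhere to the protocol requirements (eg, drug noncompliance, failure to return for study visits". A later item is a catch-all: "The investigator also has the right to withdraw patients from the study in the event of intercurrent illness, (S)AEs, and administrative or other reasons".
- Section 8.4.1 concerns leaving study drug only: "Patients permanently withdrawn from study drug should not be withdrawn from the study". Visits continue to Day 56, "except in cases where the patient has withdrawn consent for study participation". If that is not possible, the patient is asked to attend for the Early Termination and Follow-up assessments.
- Section 7.1 applies the same rule to drug discontinuation for any reason: "the patient will be asked to stay in the study and perform all the visits and assessments as planned".
- Section 9.5 defines noncompliance by the proportion of containers used between visits and adds: "Discontinuation of treatment for noncompliance is at the" investigator's discretion. It says nothing about leaving the study.

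In the SAP, Table 3 (section 7.1) classes stopping treatment for any reason other than a treatment-related adverse event or death as ICE2. It assigns this event to treatment policy and gives the following rule for the data: "Available data occurring on or after the ICE will be used for the analysis as observed. Monotone missing data will be imputed using LOCF".

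**The concern.** For the same behaviour, 9.5 read with 7.1 and 8.4.1 leads to a patient who may be off drug but is still seen at Week 8, while 8.4.2 allows the patient to be removed from the study. No section says which prevails.

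A treatment policy estimand depends on outcomes observed after treatment stops. A patient removed under 8.4.2 before Day 56 has no Week 8 central reading, even if willing to attend, and an earlier status stands in for it. Noncompliance may be linked to how the eye is doing: a patient may lose interest because the lesion is not closing, or because it has already closed. The loss can therefore be informative, and its direction cannot be predicted.

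SAP 7.2 applies the same handling to the other binary endpoints, and Table 6 uses LOCF for ICE2 in the time-to-event endpoints. Corneal sensitivity is the most exposed. Protocol Table 2 measures it at screening, Visit 8, Visit 10 and Early Termination only, so without an Early Termination visit the only earlier value is the baseline one.

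**Working it through.** **The plan's own figure.** Protocol 15.1 gives 27 per arm for 27% against 72% (a 45-point difference), two-sided alpha 0.05, about 80% power and 15% dropout.

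- Normal approximation with pooled variance under the null: n = [1.96·√(2·0.495·0.505) + 0.842·√(0.27·0.73 + 0.72·0.28)]² / 0.45² = 18.2.
- With continuity correction: (18.2/4)·[1 + √(1 + 4/(18.2·0.45))]² = 22.4, so 23 evaluable per arm.
- Dropout: 23 × 1.15 = 26.5, so 27; or 23/0.85 = 27.06, so 28. The stated 27 is reproduced to within one patient.

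The plan thus allows for about 27 − 23 = 4 patients per arm without data. That allowance concerns power. It does not address error in a status that is carried forward and counted.

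**Following one patient through each rule.** Take a patient judged noncompliant in Week 3 who is willing to keep attending.

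1. Under 9.5 the investigator may or may not stop treatment. If treatment stops, 7.1 and 8.4.1 apply: the visits continue, the Visit 8 photograph is taken, and ICE2 uses it as observed.
2. Under 8.4.2 the investigator may instead withdraw the patient from the study. Treatment ends, so ICE2 applies, but there is no Visit 8 photograph. The last available reading is carried forward. That is the Early Termination reading if the visit took place (it includes the fluorescein test and photograph, but 8.4.2 asks for these data only where possible), otherwise the last scheduled visit.
3. The only exception in 7.1 and 8.4.1 is withdrawn consent, which does not cover this patient. By its terms 8.4.1 protects patients who have already been permanently taken off drug, so a noncompliant patient still using drug can be removed under 8.4.2 without first coming under the retention rule.

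**Size per patient.** The mITT denominator is about 27 per arm, and 8.4 does not replace withdrawals. One status that differs from the true Week 8 status changes the arm's healing rate, and its difference from vehicle if it is an active arm, by 1/27 = 0.037, or 3.7 points. Against the planned 45 points that is 3.7/45 = 0.08. A wrong not-healed lowers the arm's rate and a wrong healed raises it. If the carried-forward status happens to be right, the change is zero.

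**Number of patients.** The documents give no expected rate of noncompliance or of withdrawal for it, so no arm-level total is calculated here.

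**The case against.** The strongest reply is that this is loose wording rather than a real conflict. Section 8.4.2 is permissive, and a consistent reading exists: the investigator stops treatment under 9.5, and 8.4.1 then says that the patient should remain in the study. Sections 7.1 and 8.4.1 themselves only ask patients to stay and have a fallback. The SAP foresees missing data after ICE2 and tests its handling with control-based MNAR imputation (7.1.2), observed cases (7.1.3) and a supplementary estimand with MAR imputation (7.1.1).

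Much of this stands. It limits the size of the problem but does not remove the conflict, because a site acting on 8.4.2 would be within the protocol. The additional analyses show how far the result depends on LOCF; they do not recover a reading that was never taken.

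Three stronger readings are not supported.

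- A reader might infer that the Week 8 assessment is lost whenever a patient is noncompliant. Withdrawal is optional, and an Early Termination photograph may exist, although it is not a Week 8 reading.
- A reader might infer from the 80% limit in 9.5 that removal is easily triggered, even by the Day 3 visit. Section 8.4.2 does not cite that limit; 9.2 allows fewer administrations on Day 1; Table 2 schedules no container collection at Visit 2; and 9.5 describes the Day 3 diary review as a chance to correct problems by Day 7.
- A reader might infer a total bias from the 15% dropout allowance. That figure is not broken down by reason, and some noncompliant patients would not attend Visit 8 under any wording. Those who fail to return, named in the same bullet, are already unobserved.

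**Conclusion.** The inconsistency is real and worth correcting. Protocol 8.4.2 permits an avoidable loss of the primary assessment in patients whose Week 8 outcome the primary estimand calls for, and whose reason for removal may be related to that outcome. The effect is 3.7 points on an arm's healing rate for each patient whose carried-forward status is wrong, in either direction. This assumes about 27 patients per arm in the analysis and that the removed patient would have attended Visit 8. The number of such patients is unknown, so the conclusion is that readings can be lost, not that the primary comparison is biased by any stated amount.

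**What to change.** Reconcile 8.4.2 with 7.1, 8.4.1 and 9.5.

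- Remove drug noncompliance from the study-withdrawal reasons in 8.4.2.
- Add a sentence to 8.4.2 stating that noncompliance with study drug alone does not end study visits, and that this holds also under the general nonadherence wording and the administrative-or-other clause. Without it, the open-ended list would still allow the same removal.
- State that the Visit 8 assessment is still sought unless the patient withdraws consent or is lost to follow-up.
- Leave any decision on stopping study drug as 9.5 has it.

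The cost is a protocol amendment and a site reminder. If the change is classed as substantial, 16.7.1 requires authority and ethics approval before sites apply it. The visits are already in the schedule, so no assessment is added. The benefit is limited to patients not yet withdrawn: SAP 12.4, in a document dated 31 May 2024, already reports the decision of the committee's first formal review, so part of the trial was complete by then.
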